Title Page

A Prospective, Single- Center, Phase IV Interventional, Single Arm **T**rial for the
Evaluation of subcutaneous recombinant **H**irudin 15 mg (RB variant) in
prophylaxis of Deep Vein Thrombosis (**DVT**) post major orthopedic operations

Principle Investigator: [name]

Sub Investigator: [name]

Study Site: Alexandria University

Protocol Name: THRIVE-DVT

Protocol Number: Sub-Thromb-001

Version:1.0, amendment 1

Date: 25th of January, 2022

CONFIDENTIALITY STATEMENT

This study was performed in compliance with Good Clinical Practice (GCP), including the archiving of essential documents. This report has been prepared in accordance with ICH Harmonized Tripartite Guideline on the Structure and Content of Clinical Study Reports, dated November 1995.

Any and all information presented in this document shall be treated as confidential and shall remain the exclusive property of **Minapharm Pharmaceuticals** (or any of its affiliated companies). The use of such confidential information must be restricted to the recipients for the agreed purpose and must be disclosed, published or otherwise communicated to any unauthorized persons, for any reasons, in any form whatsoever without the prior written consent of **Minapharm Pharmaceuticals** (or the concerned affiliate company); "Affiliate Company" means any corporation, partnership or other entity which at the date of communication or afterwards with **Minapharm Pharmaceuticals**

1. Synopsis

Title	Description
Study Title	Prospective, Single- Center, Interventional, Single Arm Trial for the Evaluation of subcutaneous recombinant Hirudin 15 mg (RB variant) in prophylaxis of Deep Vein Thrombosis (DVT) post major orthopedic operations
Study number	Sub-Thromb-001
Study Phase	Phase IV
Study Design	Prospective, Single arm, single-center
Study population	Patients undergoing major orthopedic operations
Study procedures	
Drug: r-Hirudin Other Name: Thrombexx
 
100 Patients will be treated with r-Hirudin (Thrombexx) for a total of 15 days beginning with 15 mg BID s.c starting 6 hours after surgery or upon adequate hemostasis and continued until end of study.

Clinical & laboratory investigations	
For Events of Deep Vein Thrombosis (DVT) within 15 days post-op.)
 
All of the patients underwent Routine bilateral compression Doppler.
 
For Clinical PE (Pulmonary Embolism) Events from Day of surgery and During Hospitalization period or end of study
 
Clinical PE events PE (Pulmonary Embolism) events were confirmed by spiral CT.
 
For follow up:
 
APTT should be done before the first dose then after 4 & 8 hours of the first dose, then on days 1,8,15 post operatively.

Study duration	
Enrolment period: 3 months duration
 
Follow-up duration: Follow-up per patient will be for a period of 15 days

Eligibility Criteria	
Inclusion Criteria:
 
 18 years of age or older Body Weight >60 kg Patients undergoing major orthopedic operations

	
Patients ready to sign informed consent form (ICF) Patients should discontinue any agents that affect haemostasis prior to the study medication use unless strictly indicated. These agents include medications such as: anticoagulants, thrombolytics, non-steroidal anti-inflammatory agents (including Ketorolac tromethamine), preparations containing aspirin, systemic salicylates, ticlopidine, dextran 40, clopidogrel, other anti-platelet agents including glycoprotein IIb/IIIa antagonists or systemic glucocorticoids.
 
Exclusion Criteria:
 
Significant bleeding injury such as solid organ laceration or intracranial bleed at discretion of attending physician Hypersensitivity to Hirudin or prior documented Allergy to its components Pregnant or breast feeding Hemorrhagic stroke in preceding 3 months abnormal baseline coagulation characterized by an INR >1.4, obtained at the discretion of the treating clinician Required therapeutic anticoagulation for atrial fibrillation, prior VTE, or mechanical heart valve Patients with a history of coagulation disorder Treatment with concomitant anti-platelet agent other than aspirin 326 mg or more daily (Platelet count < 100 X10⁹ /dl) Active bleeding Subjects with a life expectancy less than 1 month


Study objective
	
The primary objective of this study is to evaluate the efficacy of r-Hirudin RB variant 15 mg in DVT prophylaxis post major orthopedic operations
 
The secondary objective of this study is to evaluate the safety of r-Hirudin RB variant 15 mg in DVT prophylaxis post major orthopedic operations in terms of serious bleeding.

Study endpoint
	
Primary endpoint: Primary end points included new onset symptomatic thrombosis requiring medical or surgical intervention or death due to thrombosis defined as fatal PE, ischemic stroke, mesenteric thrombosis, or myocardial infarction.
 
Secondary endpoint: The Secondary end point of major bleeding is defined as clinically evident hemorrhage associated with a

	
hemoglobin decrease ≥ 2 g/dL that leads to a transfusion of ≥ 2 units of whole blood or packed red cells outside of the perioperative period (time from the start of the surgery or procedure and up to 12 hours after), or hemorrhage that is intracranial, retroperitoneal, or into a prosthetic joint. Recording serious adverse events (SAE)/ adverse events (AE) during the study duration.


Study medication
	
Thrombexx ;
 
Because thrombin plays a central role in thrombogenesis, the goal of most treatment regimens is to block thrombin generation or inhibit its activity.
 
 1- r-Hirudin binds directly with thrombin to its active & fibrinogen binding site. 2- r-hirudin does not require access to heparin binding site & can thus neutralize clot bound thrombin. Hence, down regulating thrombin generation & potentially enhancing early revascularization. 
Direct thrombin inhibitors were developed to overcome the inability of the heparin/ antithrombin complex to inactivate bound thrombin. In contrast to heparin and low-molecular-weight heparin, which catalyze the inactivation of thrombin and activated factor X (factor Xa) by antithrombin, direct thrombin inhibitors bind to thrombin and block its interaction with its substrates.
 
II- They do not bind to plasma proteins; direct thrombin inhibitors produce a more predictable anticoagulant response than heparin.
 
III- Unlike heparin, direct thrombin inhibitors do not interact with platelet factor 4 or high-molecular-weight multimers of von Willebrand factor. Consequently, the activity of direct thrombin inhibitors in the vicinity of a platelet-rich thrombus is not compromised.
 
IV- Finally, thrombin bound to fibrin or fibrin degradation products is susceptible to inactivation by direct thrombin inhibitors. Because the active site of thrombin is not involved in the interaction of the enzyme with fibrin, it remains accessible to active site-directed thrombin inhibitors. Consequently, these agents inactivate fibrin-bound thrombin without displacing the enzyme from fibrin. In contrast, bivalent thrombin inhibitors, such as Hirudin and bivalirudin, displace bound thrombin during the inhibition reaction by competing with fibrin for access to exosite 1 on thrombin.

	
Dose: In DVT Prophylaxis: 15 mg twice daily, subcutaneous for 15 days
 
In case of renal insufficiency, the dose is titrated because r-Hirudin is excreted renally. According to Creatinine clearance: •Creatinine clearance > 31-60 ml/min (5 mg s.c twice daily) •Creatinine clearance < 31 ml/min (1.7 mg s.c twice daily)

Sample size	100 patients
Statistical analysis	
- Descriptive analysis: All statistical tests used a significance level of P=0.05, two tailed tests are performed for all analyses used statistical testing. Descriptive analysis for quantitative data will include count, mean with 95% CI, standard deviation, median, minimum and maximum. For qualitative categorical variables; frequency and percentage and 95% confidence interval will be applied.

Stopping rules	
DVT PE Major bleeding Allergy APTT value increases by 2-2.5 folds According to investigator evaluation

Table of Contents

Title Page	1
1. Synopsis	2
Table of Contents	6
2. LIST OF ABBREVIATIONS	9
3. SIGNATURE(S) PAGE	10
4. INTRODUCTION	11
4.1. Background	11
4.2. Correlative studies:	11
4.3. Study Rationale	12
5. STUDY OBJECTIVES	12
5.1. Primary Objectives	12
5.2. Secondary objectives	12
6. TRIAL DESIGN	12
6.1. The pre-operative Phase	12
6.2. The operative Phase	13
6.3. The Follow-up Phase	13
7. FLOW CHARTS:	13
7.1. STUDY FLOW CHARTS:	13
7.2. STUDY PHASES	14
8. STUDY OUTCOME MEASURES	15
8.1. Primary Endpoints	15
8.2. Secondary Endpoints	16
9. STUDY POPULATION	16
9.1. Recruitment strategy:	16
9.2. Inclusion Criteria	16
9.3. Exclusion Criteria	16
10. STUDY PROCEDURE:	17
10.1. Selection of the study population:	17
10.2. Case Report Form	17
11. SOURCE DATA	17

12.	TREATMENT OF TRIAL PARTICIPANTS	18
12.1.	Description of Study Medication(s)	18
12.2.	Concomitant Medication (if applicable).....	19
13.	DATA COLLECTION	19
15.1.	DATA MANAGEMENT	20
15.2.	AMENDMENT TO THE PROTOCOL.....	20
15.2.1.	Protocol Deviations	20
15.2.2.	Onsite Audits.....	20
15.2.3.	Study Monitoring	21
15.3.	PREMATURE DISCONTINUATION OF STUDY.....	22
16.	SAFETY REPORTING AND DEFINITIONS	22
16.1.	Adverse Events Monitoring.....	22
16.2.	Reporting Period.....	23
16.3.	Adverse Event (AE):	23
16.4.	Serious Adverse Events	24
16.4.1.	Instructions for Reporting Serious Adverse Events	24
17.	STATISTICAL METHODOLOGY	24
17.1.	Determination of Sample Size.....	24
17.2.	Analysis Variables:.....	25
17.2.1.	Primary analysis variables:.....	25
17.2.2.	Secondary analysis variables:.....	25
17.2.3.	Statistical Method:.....	25
17.2.4.	Interim Analysis	25
18.	ETHICS.....	25
18.1.	INDEPENDENT ETHICS COMMITTEE (IEC) OR INSTITIUTIONAL REVIEW BOARD (IRB).....	25
18.2.	Ethical principles:	26
18.3.	Laws and regulations:	26
18.4.	PATIENT INFORMATION AND CONSENT	26
18.5.	DISCONTINUATION OF THE STUDY	27
18.5.1.	PREMATURE DISCONTINUATION OF STUDY	27

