9.3. Exclusion Criteria

Significant bleeding injury such as solid organ laceration or intracranial bleed at discretion of attending physician

Hypersensitivity to Hirudin or prior documented allergy to its components

Pregnant or breast feeding females

Hemorrhagic stroke in preceding 3 months

Abnormal baseline coagulation characterized by an INR >1.4 , obtained at the discretion of the treating clinician

Required therapeutic anticoagulation for atrial fibrillation, prior VTE, or mechanical heart valve
Treatment with concomitant anti-platelet agent other than aspirin 326 mg or more daily
Subjects with a life expectancy less than 1 month

10. STUDY PROCEDURE:

10.1. Selection of the study population:

Subjects will be selected according to inclusion and exclusion criteria, willing to sign informed consent and able to complete the study.

Subject's informed consent had to be obtained and documented in accordance with local regulations, ICH-GCP requirements, and the ethical principles that have their origin in the principles of the Declaration of Helsinki.

Prior to obtaining informed consent, information should had been given in a language and at a level of complexity understandable to the subject in both oral and written form by the investigator or designee. Each subject should have the opportunity to discuss the trial and its alternatives with the investigator. the written Informed Consent Form should have been signed and personally dated by the subject, or his legal representative, and by the person who conducted the informed consent discussion (investigator or designee). The subject or his legal representative must had received a copy of the signed and dated Informed Consent Form. As part of the consent process, each subject must have consented to direct access to his medical records for trial-related monitoring, auditing, IRB/IEC review and regulatory inspection.

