Recruitment plan will be through explaining to patients the clinical trial objective in Alexandria University hospital; referral also will be used to increase the flow rate of recruitment.

5.2 Inclusion Criteria:

Subjects meeting all of the following criteria will be considered for enrolment in the study:

1. Patients aged 18 years of age or older
2. Body Weight >60 kg
3. Patients undergoing major orthopedic operations Total knee & hip Arthroplasty
4. Patients ready to sign (ICF)
5. Patients should discontinue any agents that affect haemostasis prior to the study medication use unless strictly indicated. These agents include medications such as: anticoagulants, thrombolytics, non-steroidal anti-inflammatory agents (including Ketorolac tromethamine), preparations containing aspirin, systemic salicylates, ticlopidine, dextran 40, clopidogrel, other anti platelet agents including glycoprotein IIb/IIIa antagonists or systemic glucocorticoids.

5.3 Exclusion Criteria:

Subjects presenting with any of the following will not be included in the study:

1. Subjects with a history of hypersensitivity to any of the active ingredients of the treatments used
2. Significant bleeding injury such as solid organ laceration or intracranial bleed at discretion of attending physician
3. Hypersensitivity to Hirudin or prior documented allergy to its components
4. Pregnant or breast feeding females
5. Hemorrhagic stroke in preceding 3 months
6. Abnormal baseline coagulation characterized by an INR >1.4, obtained at the discretion of the treating clinician
7. Required therapeutic anticoagulation for atrial fibrillation, prior VTE, or mechanical heart valve
8. Treatment with concomitant anti-platelet agent other than aspirin 326 mg or more daily
9. Subjects with a life expectancy less than 1 month

6 Assessment Schedule

Subjects will be enrolled for duration of 1 months including the screening visit

- a. Preoperative phase (screening visit)
- b. Operative phase (Day 0)
- c. Visit 2: Post-operative phase (Follow-up 1(Day 1)
- d. Visit 3: Follow-up 2 (Day 8)
- e. Visit 4: Follow-up 3/ End of Study (Day 15)

7 Medicinal Products:

- Thrombexx Ampoules (r-Hirudin 15mg/ ml pro inject **S.C. only**)

8 Statistical Methodology:

8.1 Determination of Sample Size:

Sample size: Records for 100 patients who underwent major orthopedic surgery collected from 1 site

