9.1.5 Lab Results

Table 6 Mean of Lab Results at baseline visit

	N = 100
Was the lab report received? N (%)	
Hb%, Mean ± SD, (g/dL)	
Platelets Count, Mean ± SD, (x10³/μL)	
APTT, Mean ± SD, (seconds)	
INR, Mean ± SD	
SGPT, Mean ± SD, (IU/L)	
SGOT, Mean ± SD, (IU/L)	
Sr. Albumin, Mean ± SD, (g/dL)	
Sr. Bilirubin, Mean ± SD, (mg/dL)	
Sr. Creatinine, Mean ± SD, (mg/dL)	
Creatinine Clearance, Mean ± SD, (ml/min)	
RBS, Mean ± SD, (mg/dL)	

Table 7 *Number and percent of Surgery Information*

		N = 100
Type of Surgery	Surgery 1, N (%)	
	Surgery 2, N (%)	
	Surgery 3, N (%)	
Type of Anesthesia	Anesthesia 1, N (%)	
	Anesthesia 2, N (%)	
	Anesthesia 3, N (%)	
Patient Position	Position 1, N (%)	
	Position 2, N (%)	
	Position 3, N (%)	
Type of prosthesis	Prosthesis 1, N (%)	
	Prosthesis 2, N (%)	
	Prosthesis 3, N (%)	
Blood Transfusion	Transfusion 1, N (%)	
	Transfusion 2, N (%)	
	Transfusion 3, N (%)	

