9.3 Secondary End Point

Table 11 Proportion of patients experienced major bleeding

		Day 1	Day 8	Day 15	p-value
Assessment of Bleeding:	Normal, N (%)				
	Abnormal, N (%)				
Type Of Blood Transfusions:	Whole Blood, N (%)				
	RBCs, N (%)				
	Platelets, N (%)				
	Plasma, N (%)				

Table 12 *Number and percent of Adverse Event among treatment groups*

	N = 100	p-value
Total No of AE, N (%)		
AE1, N (%)		
AE2, N (%)		
AE3, N (%)		

Table 13 *Number and percent of Serious Adverse Event among treatment groups*

	N = 100	p-value
Total No of SAE, N (%)		
SAE1, N (%)		
SAE2, N (%)		
SAE3, N (%)		

Table 14 *Percent Change in mean Hb%*

	Screening	Day 1	Day 8	Day 15	p-value
Hb%, (mean ± SD)					
% change					
p-value					

Table 15 *Percent Change in mean Platelets count*

	Screening	Day 1	Day 8	Day 15	p-value
Platelets count, (mean ± SD), x 10³/μL					
% change					
p-value					

Table 16 *Percent Change in mean Systolic BP*

	Screening	Day 0	Day 1	Day 8	Day 15	p-value
Systolic BP, (mean ± SD), mmHg						
% change						
p-value						

Table 17 *Percent Change in mean Diastolic BP*

	Screening	Day 0	Day 1	Day 8	Day 15	p-value
Diastolic BP, (mean ± SD), mmHg						
% change						
p-value						

Table 18 *Percent Change in mean Sitting Pulse Rate*

	Screening	Day 0	Day 1	Day 8	Day 15	p-value
Sitting Pulse Rate, (mean ± SD), beats /min						
% change						
p-value						

Table 19 *Percent Change in mean Oral Temperature*

	Screening	Day 0	Day 1	Day 8	Day 15	p-value
Oral Temperature, (mean ± SD), °C						
% change						
p-value						

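### Three exclusions in the protocol synopsis (coagulation disorder, low platelets, active bleeding) are missing from protocol 9.3 and SAP 5.3, and the platelet limit is printed in a unit that cannot be applied as it stands

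*Protocol*

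**What the plan says.** Exclusion criteria are given in three places.

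- **Protocol synopsis.** Among its exclusions are "Patients with a history of coagulation disorder" and, after the anti-platelet item, "Platelet count < 100 X10⁹ /dl) Active bleeding".
- **Protocol 9.3.** Its nearest item to active bleeding is "Significant bleeding injury such as solid organ laceration or intracranial bleed at discretion of attending physician". It also excludes an INR above 1.4. It has no item on a past coagulation disorder, the platelet count or active bleeding.
- **SAP 5.3.** The list is numbered 1 to 9. Item 8 is "Treatment with concomitant anti-platelet agent other than aspirin 326 mg or more daily" and item 9, the last, is "Subjects with a life expectancy less than 1 month". None of the three synopsis exclusions appears.

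On how the lists are used, protocol 10.1 says only: "Subjects will be selected according to inclusion and exclusion criteria, willing to sign informed consent and able to complete the study". Protocol 6.1 likewise refers to the criteria in general terms. Neither points to one list.

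The SAP reports platelets per µL: "Platelets Count, Mean ± SD, (x10³" in Table 6 and "Platelets count, (mean ± SD), x 10³" in Table 15.

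**The concern.** All three missing items concern bleeding risk, and the study drug is an anticoagulant. If the lists differ, the same patient can be a wrongful enrolment under one part of the protocol and a valid one under another. Monitors must check conduct against the approved protocol (15.2.3) and deviations must be reported to the ethics committee (15.2.1). Neither can be done consistently while the protocol carries two lists.

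The analysis is touched as well. The proportion of patients with major bleeding is a secondary analysis variable (protocol 17.2.2, SAP 8.2.2), and the three criteria help to decide who is in its denominator.

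The unit is a separate difficulty. Copying the synopsis line into the other two lists would not settle the matter, because the limit as printed does not fit the scale on which the trial reports platelets.

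**Working it through.** **Step 1. Compare the lists item by item.**

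| Exclusion | Synopsis | Protocol 9.3 | SAP 5.3 |
|---|---|---|---|
| Significant bleeding injury | yes | yes | yes |
| Hypersensitivity to hirudin | yes | yes | yes |
| Pregnancy or breast feeding | yes | yes | yes |
| Recent hemorrhagic stroke | yes | yes | yes |
| INR above 1.4 | yes | yes | yes |
| Need for therapeutic anticoagulation | yes | yes | yes |
| Past coagulation disorder | yes | **no** | **no** |
| Anti-platelet agent | yes | yes | yes |
| Platelet limit | yes | **no** | **no** |
| Active bleeding | yes | **no** | **no** |
| Short life expectancy | yes | yes | yes |
| General hypersensitivity item | no | no | yes |
| Total | 11 | 8 | 9 |

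Check: 11 − 3 = 8 for 9.3, and 8 + 1 = 9 for the SAP. The synopsis total depends on how run-together text is read. The platelet limit stands in parentheses after the anti-platelet item; if it belongs to that item, the synopsis has 10 items. The same three conditions are absent elsewhere on either reading.

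**Step 2. Could the items have been lost when the text was extracted?** SAP 5.3 is numbered without a gap, and its item 8 is followed directly by item 9. Protocol 9.3 gives its items in the same order. Loss in extraction is not a plausible explanation.

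**Step 3. Do the retained items cover the gap?**

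- Past coagulation disorder: the INR criterion catches some such patients. It is a baseline value, taken at the clinician's discretion, and does not capture a history.
- Active bleeding: the bleeding-injury item overlaps with it, but its examples are organ laceration and intracranial bleeding, and it is left to the physician's discretion.
- Low platelets: no item in 9.3 or SAP 5.3 uses the count, although protocol 6.1 and 7.2 have it measured at screening.

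**Step 4. Convert the printed platelet limit.** Inputs are 100×10⁹ per dl (synopsis), 1 dl = 10⁵ µL and 1 L = 10⁶ µL.

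- As printed: 100×10⁹ ÷ 10⁵ = 10⁶ per µL = 1,000×10³/µL.
- Same number read per litre: 100×10⁹ ÷ 10⁶ = 10⁵ per µL = 100×10³/µL.
- Ratio: 1,000 ÷ 100 = 10.

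Taken literally, the synopsis would exclude everyone below 1,000×10³/µL.

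**The case against.** The best case on the other side is that a synopsis only summarises, that 9.3 is the operative list and agrees with SAP 5.3 on these three points, and that other safeguards exist: the INR criterion, the bleeding-injury item, dosing that waits for adequate hemostasis (synopsis, 6.2), and major bleeding among the stopping rules. Part of this stands. It would be too strong to say that patients with a coagulation disorder or active bleeding are freely admitted under 9.3 and SAP 5.3, because there is partial cover. But here the summary is stricter than the section it summarises, no text ranks the lists, and the low-platelet patient has no cover at all.

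Three stronger readings may tempt a reader, and the documents do not support them.

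- **That the mismatch shifts the major-bleeding result by a known amount.** The documents do not say how many patients would be classified differently, so no effect on the proportion can be calculated.
- **That the spinal-anesthesia sentence in 12.1 contradicts the start of treatment.** The synopsis, 6.2 and SAP 2.2 start the drug after surgery. Read literally, 12.1 has a dose 8-10 hours before puncture, but the sentence may only space doses around puncture or catheter removal. Protocol 7.1 and 7.2 do not decide it: they place the first dose on Day 0 without saying before or after surgery, and the empty pre-operative column in 7.1 is the screening visit. This is an ambiguity.
- **That 15 days breaches the label.** Section 4.1 cites 9-12 days from the package insert, so 15 days is 15 − 12 = 3 to 15 − 9 = 6 days longer. However, 6.1 and SAP 2.1 also allow the regimen to follow standard clinical practice, and the label aspects they name are dose, population and indication, not duration. The insert itself is not available here.

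**Conclusion.** The exclusion lists are inconsistent as written, and this should be corrected. Three synopsis exclusions are missing from both protocol 9.3 and SAP 5.3, and no rule of precedence exists. The clearest case is the patient with low platelets, who can be excluded by one list and eligible under two. The printed limit equals 1,000×10³/µL, ten times a per-litre reading, and cannot be applied without interpretation. That litres were meant is an assumption that only the sponsor can confirm.

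Confidence is high on the list comparison and the unit conversion, since both rest on the text alone. The consequence for safety and for the major-bleeding population is real in kind but of unknown size. The spinal-anesthesia and duration wording is a minor request for clarification.

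**What to change.** 1. Reconcile the synopsis, protocol 9.3 and SAP 5.3 into one identical exclusion list. The sponsor decides whether each of the three items is kept. The general hypersensitivity item found only in SAP 5.3 should be settled at the same time.
2. If the platelet criterion is retained, confirm its value and unit and print it in ×10³/µL, as in SAP Tables 6 and 15.
3. As a minor clarification, reconcile the 12.1 spinal-anesthesia sentence with the post-surgery start in the synopsis, 6.2 and SAP 2.2. Also reconcile the 15 days in the synopsis and 12.1 with the 9-12 days cited in 4.1 and the label wording of 6.1 and SAP 2.1. No clinical rule is proposed here.

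The cost is mainly wording in one protocol amendment and the matching SAP text. Platelet count and medical history are already collected at screening. If active bleeding is kept as an exclusion, the flow chart may also need an entry, because 7.1 has no bleeding assessment at screening (the first is on Day 0).
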